**I.    Hypotheses**

Multiple sclerosis (MS) is a progressive disabling disease of the central nervous system (CNS) which is associated with substantial personal, financial and societal costs. There now are 15 approved disease modifying therapies (DMTs) available, and data supports that early intervention is associated with best outcomes. The ultimate cause of MS remains unknown, but increased risk is associated with a host of genetic and environmental factors. First degree relatives (FDRs) of MS patients have a 10-20 fold increased risk of being diagnosed with MS themselves. But diagnosis, still, is delayed for many, in part due to lack of a specific biomarker of disease activity, and also due to vagueness of early symptoms in many. More recent studies, have clearly outlined a prodrome in individuals ultimately diagnosed with MS, prior to overt clinical symptoms typical of MS. Thus, it would be extremely helpful if we could develop a risk stratification algorithm that outlined those with both high and low risk of developing MS as early as possible in the disease process. The central hypothesis of this protocol is that it is possible, using FDRs of patients with MS and assessing a variety of both known and unknown risk factors for MS, to define a risk algorithm for earliest signs of development of MS. In addition, while starting with a relatively limited cross-sectional analysis, we hypothesize that development of a larger, longitudinal study will allow us to improve sensitivity by simple accrual of larger numbers of participants over time with the endpoint of early signs of MS on MRI scans, but also improve sensitivity by adding additional markers of MS risk as they become available.

**II.    Specific Aims**, among asymptomatic first degree relatives (FDRs), aged 18-30, of multiple sclerosis (MS) patients:

- 1: Determine the prevalence of brain MRI lesions disseminated in space (DIS), consistent with MS
- 2: Gather data on potential risk factors or early signs related to MS development, including markers for: genes, immunological function, environmental factors, neuroaxonal damage, Vitamin D levels, lipid metabolism, activity levels, mood abnormalities, and cognitive function. From this, develop a risk factor score, incorporating all relevant potential markers of increased risk of DIS.

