Innovation – The GEMS study described above is one approach to identification of early MS, but it had several limitations. It used a pre-defined risk score, including a SNP analysis of just 64 SNPs, when more recent analysis suggests over 200 may be relevant. It employed a long, detailed, and expensive brain MRI, but did not include spine or FLAIR\* analysis. The cost limited participation. GEMS did not include potential immunological markers, markers of CNS damage (such as NFL or lipids), activity levels, or a detailed environmental screen. Due to privacy issues, they were unable to verify the MS diagnosis in FDRs. Finally, it was limited to 100 patients, of which only 65 (females only) were analyzed. Other studies (as yet unpublished) designed to look at risk factor algorithms for development of MS are employing larger numbers of patients, but minimal, if any, MRI analyses, no or minimal immunological or CNS damage markers, and no activity levels. Most importantly, they are using full clinical diagnosis of MS as the outcome measure, greatly limiting the number of “positive” patients, and biasing toward a much later time in the disease process. Thus, our study has great innovative value for several reasons:

- a. We will define pre-symptomatic MS in 300 FDRs using stringent MRI criteria, including FLAIR\* sequences, thus significantly increasing sensitivity and detection in the prodromal phase. Proband MS patients will be defined from our own population of MS patients known to fulfill formal diagnostic criteria for MS.
- b. We will analyze genetic, immunological, vitamin, lipid, viral, and CNS damage markers; activity levels; and a mood and cognitive screen, with the goal of defining an expanded risk stratification scheme, not a pre-defined one
- c. We will include a detailed environmental screen, employing approaches very similar to the DAISY study, and [name], lead epidemiologist in DAISY, will participate as a Co-PI.
- d. We will compare those FDRs with and without brain MRI abnormalities to each other, and to non-FDR controls (blood and environmental screen, not MRI)
- e. We will create a biobank of blood, both plasma and PBMCs, including pre-processed serum/plasma and RNA, allowing us to add to the risk stratification model over time.

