The sequences were specifically chosen to: a) screen brain with the greatest specificity (FLAIR\*); b) allow for later volumetric analysis of the brain; and c) use the most sensitive technique for cortical and subcortical brain lesions (3D-DIR).

**B. Description of Population to be Enrolled:** The population will be a total of 300 women and men, of all races and ethnicities, between the ages of 18-30, inclusive, who have no symptoms of MS, but have at least one FDR with documented MS fulfilling McDonald 2017 criteria. Up to 1000 will be screened for inclusion, but some will be excluded due to inability to undergo a brain/spine MRI or have blood drawn, lack of interest after discussion of study requirements, or symptoms concerning for MS (the latter will be referred to a qualified neurologist for evaluation). FDRs with one or more siblings/parents with MS will be included, and more than one FDR of a proband MS patient will be allowed. A control group (based on # of FDRs with positive MRIs - we anticipate 15-30) of age- and sex-matched controls who have no known family members with MS (out to first cousins and grandparents) will have blood drawn and fill out the environmental questionnaire, but will not undergo a brain MRI. The controls will be matched 1:1:1 for those FDRs with positive MRI scans suggesting pre-symptomatic MS and those age-and sex-matched FDRs who do NOT have positive MRI scans suggesting pre-symptomatic MS. The ages were specifically chosen so as to have a good opportunity to collect an adequate number of MRI-positive, asymptomatic participants prior to the known median age of MS clinical onset (30 years), but not so young as to lower the likelihood of detecting asymptomatic brain MRI lesions.

1. FDR Inclusion Criteria
  - a. Male and female
  - b. All races and ethnicities
  - c. Ages 18-30
  - d. Must have a parent, sibling or child with MS fulfilling McDonald 2017 criteria
  - e. No symptoms suggestive of MS on formal screen
  - f. Ability to undergo a non-contrast MRI and venipuncture, and perform an environmental screen, mood screen and cognitive test
2. FDR Exclusion Criteria
  - a. Symptoms suggestive of MS on formal screen
  - b. Prior diagnosis of autoimmune disease that may be associated with CNS dysfunction and MRI lesions, e.g. Sjogren's
3. Non-FDR Inclusion Criteria
  - a. Male and female
  - b. All races and ethnicities
  - c. Ages 18-30

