### **C. Study Design and Research Methods:**

1. Prescreen FDRs by phone for ability to participate and lack of MS symptoms, using a standardized script to exclude those with overt MS symptoms. Proband MS patients will have documented MS by McDonald 2017 criteria.
2. Qualified FDRs will be scheduled for a study visit after completing a pre-screening questionnaire by phone. If they are not excluded by pre-screen, and wish to participate, a study visit will be scheduled. A waiver of documentation of consent will be obtained over the phone so as to instruct participants to fast from midnight prior to the first study visit. This will also allow them to fill out the environmental questionnaire on-line before their visit and at their convenience. The environmental survey must be completed at least three days prior to their visit. If not, the study visit will be canceled and rescheduled once its complete.
3. A study visit will include (See Table of activities below):
  - a. Read, ask questions regarding, and sign the consent.
  - b. Document completion of environmental questionnaire.
  - c. Obtain a measured height and weight, and compute a Body Mass Index (BMI)
  - d. Perform a non-contrast brain MRI (per section V.A)

- e. Perform a fasting Blood draw consisting of no more than 100 ccs of blood.
  - i. Blood drawn at the primary study visit will be a maximum of 100 ccs to be processed in the following fashion. Participants will not be made aware of their blood sample results
    - 1. 30 ccs for immediate cell sort by [name] into T and B lymphocytes, for CD40 expression studies, requiring primary analysis with fresh cells, and done on all samples. Also for HLA analysis.
    - 2. 20 ccs processed for delayed analysis of SNPs, viral serologies (Herpes Simplex Virus 1 and 2, Cytomegalovirus, Varicella-Zoster Virus, and Epstein-Barr Virus), vitamin D levels, and neuroaxonal (NfL - Quanterix) and myelin damage (lipids), which all can be performed on stored samples.
    - 3. 50 ccs processed and stored for delayed analysis of plasma and PBMCs, RNA and DNA, for studies not yet determined
- f. Perform the Perceived Stress Scale and the Neuro-QoL screen for anxiety and depression;
  - i. Participants screening for concerns for suicidality on the mood screen will be referred to an emergency room for evaluation.
- g. Perform a Symbol Digit Modality Test, a screen for cognitive function. The latter will be done in the written format.

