  - i. Participants will not be advised of Cognitive screen results.
- h. As a measure of physical activity, we will use Godin Leisure-Time Exercise Questionnaire (GLTEQ), which measures mild, moderate and strenuous physical activity during a typical seven day period. This has been validated in MS, and is scored either into three levels of activity (sedentary, moderately active, or active), or may be used as a continuous measure.
- i. As a dietary assessment, we will use the Harvard 2007 Booklet FFQ, which is a semi-qualitative food frequency questionnaire used to assess intake of various nutrients over the past year. This has been robustly validated in a variety of populations, and nutrient intakes are computed by assigning a daily frequency weight.

4. MRIs will be read by a board-certified neuroradiologist ([name]) with extensive experience in reading brain MRIs in general, and MS MRIs in particular. All FDRs will receive a follow-up contact concerning the results of their MRI within one week. FDRs with a brain MRI fulfilling criteria for DIS will be referred to a qualified neurologist to determine if they should be treated or monitored more closely. Individuals with abnormal brain MRI scans not suggestive of or fulfilling DIS criteria, but having non-specific brain lesions (as can be seen with migraine and many other conditions), also will be referred to a qualified neurologist for evaluation as needed. Those FDRs with unexpected abnormalities (e.g. severe sinus disease, pineal cyst, pituitary abnormality, cavernous angioma, etc.) will be referred as necessary to a qualified physician.

5. FDRs with a positive brain MRI showing lesions DIS will be asked to return within four months for a repeat blood draw of no greater than 100 cc of blood, to be compared to age-and sex-matched FDRs without a positive brain MRI (who will also be asked to return within 4 months for the repeat blood draw) and age-and sex-matched non-FDRs, both in a 1:1 ratio. The former will be identified from those already in the study, and the latter will be recruited from age- and sex-matched friends of the FDRs with positive brain MRIs. The non-FDRs will be prescreened and perform all the study procedures as the FDRs on the first study visit, with the exception of the MRI.

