- c. Aim 2. Association analyses; with individual factors and in a multiple risk factor analysis. In previous studies, HLA type, Vitamin D levels, Epstein Barr Virus exposure, smoking and early adult obesity have conferred a maximum odds ratio of 2-3 (many SNPs confer an odds ratio of 1.1-1.4) of developing MS when studied individually. In the GEMS study, participants were stratified into high and low risk categories based on a deep phenotyping of 64 SNPs, and environmental screen (including sex). Comparative analyses were performed on the high and low risk groups for both neurological exam and MRI measures. In this study, we plan to use the known risk factors, and add potential biomarkers (e.g. NfL, lipid levels) to define the risk of DIS in this population. For the power analysis we made the assumption that no single marker would exhibit an odds ratio greater than 2 for increased risk of DIS, and that all markers are additive. In this early proof of concept phase, with an estimated case sample size of 30 with 60 age- and sex-matched controls, our priori power analysis suggests an expected power ranging from 20-33% for risk factors such as smoking, obesity, and vitamin D deficiency. Using frequency and odds ratio from the GEMS study (OR = 2.9) we expect a power of 64% to detect an effect of HLA type risk. While this study will be statistically underpowered, and estimates will be imprecise, we expect that some results will have clinical significance. We plan to use these results and stored samples as the groundwork for larger, longitudinal, multi-site studies. These future studies will allow us to enroll samples sizes of greater than 500, necessary to reach 80-90% power. In reality, it is possible the effect some factors may depend on the levels of other factors. Example hypothesis that we will test: FDRs with DIS lesions are more likely to have been exposed to EBV as indicated by elevated EBV serology than FDRs of the same age and sex without DIS lesions. By extension, we will then define a risk score combining factors that are discriminatory, e.g. Vitamin D level, smoking, obesity, elevated NfL levels, impaired B cell anergy, and HLA type may each have a roughly 2 fold increased risk, whereas those with four of these factors have a six-fold increased risk of DIS on MRI.
- d. Aims 3 and 4 do not have statistical implications.

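### The stated power (20-33%, and 64% for HLA) is for 30 cases v 60 controls, but the DIS-positive v DIS-negative FDR contrast has at most 30 matched controls and no power is given for it

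*Combined protocol and SAP*

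**What the plan says.** Section V.F, item c bases its power on a study "with an estimated case sample size of 30 with 60 age- and sex-matched controls". It gives 20-33% for factors such as smoking, obesity and vitamin D deficiency, assuming no single marker exceeds an odds ratio of 2. It gives 64% for HLA type at an odds ratio of 2.9.

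The make-up of the controls is set elsewhere:

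- V.B: "The controls will be matched 1:1:1 for those FDRs with positive MRI scans", that is, one DIS-negative FDR and one non-FDR per case.
- V.C.5: DIS-negative FDRs and "age-and sex-matched non-FDRs, both in a 1:1 ratio".
- V.F.a: two controls per case, one from each group; the non-FDRs are not scanned. The expected number of cases is 15-30, from 5-10% of 300.

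On what is to be compared, item d of the Innovation list in section III says: "We will compare those FDRs with and without brain MRI abnormalities to each other, and to non-FDR controls". Aim 2 is to "develop a risk factor score, incorporating all relevant potential markers of increased risk of DIS". The one worked hypothesis in V.F.c sets FDRs with DIS against FDRs of the same age and sex without DIS. The same item concedes that the study is underpowered and its estimates imprecise.

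**The concern.** With 30 cases, the 60 controls are 30 DIS-negative FDRs plus 30 non-FDRs of unknown DIS status, chosen for having no family history of MS. No passage says the two groups are pooled, and the Innovation list treats them as two comparisons. The question in Aim 2 is which markers go with DIS among FDRs. The matched design answers it with one control per case, so the printed power belongs to a comparison with twice as many controls. It also uses the top of the plan's own range of cases.

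Alpha, sidedness and the non-HLA exposure frequencies are not given. For HLA a source is cited but the frequency is not printed, so a reader cannot adjust the figures. The same paragraph caps every single marker at an odds ratio of 2 and then powers HLA at 2.9.

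The results are meant as groundwork for larger multi-site studies. Power figures carried forward should describe the contrast that will be analysed.

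**Working it through.** **Inputs from the plan.** 30 cases and 60 controls, odds ratios 2 and 2.9, stated power 20-33% and 64% (V.F.c). One control of each type per case (V.B, V.C.5, V.F.a). 15-30 cases among 300 FDRs (V.F.a).

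**Assumptions, not in the plan.** Two-sided alpha 0.05. Exposure p0 in controls of 10-40% for odds ratio 2 and 25-45% for 2.9. Independent participants.

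**Step 1: the plan's own figure.** Case exposure is p1 = OR·p0 / (1 − p0 + OR·p0). The usual two-proportion power is Φ[(p1 − p0 − 1.96·S0)/S1], with S0 = √[p̄(1 − p̄)(1/n1 + 1/n0)], S1 = √[p1(1 − p1)/n1 + p0(1 − p0)/n0], and p̄ the pooled exposure.

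- OR 2, p0 = 0.30, 30 v 60: p1 = 0.60/1.30 = 0.4615; p̄ = 0.3538; S0 = 0.1069; S1 = 0.1086. (0.1615 − 0.2095)/0.1086 = −0.442, so power is 32.9%. At p0 = 0.10 it is 21.2%.
- OR 2.9, p0 = 0.30, 30 v 60: p1 = 0.87/1.57 = 0.5541; p̄ = 0.3847; S0 = 0.1088; S1 = 0.1083. (0.2541 − 0.2132)/0.1083 = 0.377, so power is 64.7%.

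These agree with the stated 20-33% and 64%. Because alpha and exposure are assumed, this shows consistency and does not prove how the plan's figures were obtained.

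**Step 2: the same calculation with 30 DIS-negative FDRs.** At p0 = 0.30:

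- OR 2: S0 = 0.1254, S1 = 0.1236, (0.1615 − 0.2458)/0.1236 = −0.682, power 24.8%.
- OR 2.9: S0 = 0.1277, S1 = 0.1234, (0.2541 − 0.2503)/0.1234 = 0.031, power 51.2%.

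**Step 3: matched-pair (McNemar) power.** A pair is discordant with probability p1(1 − p0) + p0(1 − p1). In a discordant pair the case is the exposed member with probability OR/(1 + OR). Power is the sum, over the binomial number m of discordant pairs, of the chance that |2X − m|/√m ≥ 1.96, where X is the number of those pairs with the case exposed. At p0 = 0.30 and OR 2, the discordant probability is 0.4615 × 0.70 + 0.30 × 0.5385 = 0.485. About 14.5 of 30 pairs are then informative, and power is 23.6%.

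| Contrast | OR 2 | OR 2.9 |
|---|---|---|
| Stated in the plan | 20-33% | 64% |
| 30 v 60, unmatched | 21-34% | 63-65% |
| 30 v 30, unmatched | 15-26% | 49-52% |
| 30 pairs, McNemar | 13-25% | 47-51% |
| 30 pairs, exposure correlation 0.2 within pairs | 11-20% | 36-40% |
| 15 v 15, unmatched | 9-15% | 27-29% |
| 15 pairs, McNemar | 8-13% | 24-26% |

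**Step 4: can any exposure frequency rescue the stated figures?** Over all p0, 30 v 30 peaks at 26.1% (OR 2) and 52.3% (OR 2.9); 30 McNemar pairs peak at 25.3% and 51.1%. The lower stated value of 20% can be reached; 33% and 64% cannot. Reaching 64% at OR 2.9 takes about 40-43 pairs, and 33% at OR 2 takes at least 39.

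**Step 5: how likely are enough cases?** With a binomial count among 300, the chance of at least 30 cases is 53% at 10% prevalence, 7% at 7.5% and 0.03% at 5%. The chance of at least 40 is about 4% at 10%, and under 0.1% at 7.5% or 5%.

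**Step 6: one-sided testing.** At one-sided 0.05, 30 pairs give 61-64% for HLA, but 30 v 60 gives 74-76%. One-sided testing therefore does not fit the stated basis of 60 controls.

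**Step 7: the odds-ratio cap.** With HLA held to the plan's own cap of 2, power is at most 34% at 30 v 60 and 25% with 30 pairs.

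**The case against.** Four points can be made for the plan.

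- **It names no main contrast.** The FDR comparison is given as an example, and 30 v 60 is a literal reading of two controls per case. Section V.F neither pools the groups nor says they are kept apart. This stands as a remark on the wording. But the outcome is DIS, which is unknown in the non-FDRs, and the Innovation list separates the comparisons. Pooling would mix association with DIS and familial risk, especially for HLA.
- **Thirty FDR controls is a limit of the matching, not of the data.** Every FDR has an MRI, blood draw, BMI and questionnaires at Visit 1. Comparing 30 cases with 270 DIS-negative FDRs gives about 31-44% at odds ratio 2 and 77-79% at 2.9, so on that basis the stated figures are not too favourable. This is true and is used in the fix. It is not the design in V.F.a, and B cell anergy and cytokines are measured only in the Visit 2 subset, where one control of each type per case is a hard limit.
- **The size of the shortfall rests on assumptions.** It does. Under a two-sided 5% test, however, the ceilings in step 4 do not depend on exposure frequency.
- **The plan already admits low power, and the 300 is not derived from these figures.** This limits the consequence. A general caveat does not correct specific numbers that refer to another comparison.

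**Conclusion.** The concern holds. The stated power is for 30 v 60, the matched FDR contrast has at most 30 controls, and no power is given for it. At two-sided 0.05 with independent participants, power for that contrast is about 13-25% instead of 20-33% at odds ratio 2, and about 47-51% instead of 64% for HLA. At 15 cases it is 8-13% and 24-26%. The assumed exposure ranges fix these intervals, but the finding that 33% and 64% are out of reach with 30 pairs holds at any exposure frequency under a two-sided 5% test. The figures ignore family clustering, although V.B says "more than one FDR of a proband MS patient will be allowed". The correction should be made, but the consequence is moderate: the study is a declared pilot, and its conclusion that it is underpowered does not change.

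**What to change.** 1. In V.F.c, restate power for the matched FDR contrast at both ends of the case range, with a matched-pair method. Suggested text: *For DIS-positive v 1:1 matched DIS-negative FDRs (matched-pair test, alpha [ ], [one/two]-sided, exposure [ ]% in DIS-negative FDRs), power with 15 and 30 pairs is [ ]% and [ ]% at odds ratio 2, and [ ]% and [ ]% for HLA at odds ratio [ ].*
2. Limit the cap of 2 to non-HLA markers, or quote HLA at 2.
3. State that the non-FDR comparison is reported separately and not pooled with the FDR controls. While editing, replace the term case-cohort in V.C.6 with the nested case-control design of V.F.a; this is a clerical correction, since V.C.6 refers back to the controls already described.
4. For data held on every FDR at Visit 1 (questionnaire items such as smoking, and measured BMI), add a comparison of cases with all DIS-negative FDRs, adjusted for age and sex. Unadjusted power at odds ratio 2 is about 31-44% with 30 v 270 and 22-28% with 15 v 285. Extend it to blood markers only if they are assayed in all FDRs. V.C.3.e says of vitamin D, SNPs, viral serologies, NfL and lipids "which all can be performed on stored samples", which does not settle that; its wording for HLA leans towards all samples but is not conclusive.

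A sentence on whether a matched control may be related to the case, and on how family clustering is handled, would help but is optional.

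**Cost:** wording, one recalculation and one added analysis of data already collected. No extra participants are needed, and no extra assays if item 4 stays with questionnaire and BMI data. The printed power for the matched contrast becomes less favourable.

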- a. This blood draw will be for B cell anergy and cytokine studies in [name] lab, and repeat CD40 studies on non-FDR controls (i.e. not already done by [name] lab) which require fresh cells, but done only on this subset of participants. The rest of the blood will be processed and stored as described in C3ei.3 above for potential future use.

6. Data will be stored in a HIPAA-compliant database. Analysis will be done via case-cohort approach with the roughly 15-30 MRI-positive participants, controls as noted, and looking at the markers individually and together.

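### The Aim 2 risk score is built from whichever of about 20 or more markers look discriminatory in 15-30 DIS cases, with no selection rule, multiplicity control, validation or failure criterion

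*Combined protocol and SAP*

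**What the plan says.** Section I makes it the central hypothesis that it is possible, in first-degree relatives (FDRs), "to define a risk algorithm for earliest signs of development of MS". Section II, Aim 2, collects markers of "genes, immunological function, environmental factors, neuroaxonal damage, Vitamin D levels, lipid metabolism, activity levels, mood abnormalities, and cognitive function" and from them develops a risk factor score for DIS.

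Three places say how the score is to be made:

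- Section III, Innovation item b, states that its content will come from the data: "with the goal of defining an expanded risk stratification scheme, not a pre-defined one".
- Section V.C, item 6, describes the analysis as "looking at the markers individually and together".
- Section V.F.c gives the plan for Aim 2 as "Association analyses; with individual factors and in a multiple risk factor analysis", and then: "By extension, we will then define a risk score combining factors that are discriminatory".

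Section V.F.c also concedes that the study is underpowered and its estimates imprecise, and adds that "we expect that some results will have clinical significance". Sections V.E and V.F.c call the work a proof of concept and leave adequate power to larger studies.

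Nowhere do the documents state an alpha, a threshold for a discriminatory factor, an adjustment across markers, a global test, a performance measure, internal or external validation, or a result that would count against the hypothesis.

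**The concern.** A score made of the markers that stand out in one small sample will contain some that stand out by chance. Judged in that same sample, it will appear to separate cases from controls even if none of its components is related to DIS. Low power is a different problem: it concerns real effects that are missed, and the plan admits it. False selection concerns effects that are not there, and the plan does not address it.

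At stake is how the Aim 2 result can be read. The results are meant to support the design of larger multi-site studies (Aim 3 and V.F.c). Without a rule that separates signal from noise, readers cannot tell a promising score from one that chance would produce. Aim 1 (prevalence, descriptive) and the biobank are not affected.

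**Working it through.** **1. The plan's own figures.** V.F.c writes "our priori power analysis suggests an expected power ranging from 20-33" per cent for single risk factors at an odds ratio of 2, and 64% for HLA at 2.9, with 30 cases and 60 controls. Alpha and exposure frequencies are not given, so strict reproduction is not possible. Let p0 be the exposure frequency in controls. With p1 = OR·p0/(1 − p0 + OR·p0) and a two-sided 5% comparison of two proportions, 30 v 60:

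- OR 2: power 0.21 at p0 = 0.10, 0.29 at 0.20, 0.33 at 0.30.
- OR 2.9: power 0.63 at p0 = 0.25, 0.65 at 0.30.

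The stated figures are consistent with a two-sided 5% test. A one-sided 5% test also gives about 20-33% at OR 2 for p0 of about 0.05-0.12, so alpha cannot be recovered. Two-sided 5% is assumed below.

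**2. Number of markers.** Sections III, V.C and V.F name 22 measures besides SNPs: HLA; vitamin D; EBV, HSV-1, HSV-2, CMV and VZV serology; NfL; total cholesterol, LDL and HDL; CD40; B cell anergy; cytokines; BMI; smoking; stress; anxiety; depression; SDMT; GLTEQ; diet. Counting lipids as one and adding SNPs as one gives 22 − 2 + 1 = 21. Testing SNPs, nutrients or cytokines singly raises the count.

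**3. Chance of false selection when no marker is related to DIS.** For k independent tests at 5%, P(at least one) = 1 − 0.95^k and P(at least two) = 1 − 0.95^k − k·0.05·0.95^(k−1).

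| k | At least one | At least two | At least four |
|---|---|---|---|
| 15 | 54% | 17% | 0.6% |
| 20 | 64% | 26% | 1.6% |
| 22 | 68% | 30% | 2.2% |
| 30 | 79% | 45% | 6.1% |

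The expected number of false selections at k = 22 is 22 × 0.05 = 1.1.

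**4. Sensitivity of the at-least-one figure.**

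- Common correlation of 0.1/0.3/0.5/0.7 among 20 markers (simulated): 63%/54%/42%/29%.
- 20 binary markers by Fisher's exact test, 30 v 60, true size 0.031-0.040: about 47-56%.
- 22 binary markers by Fisher's exact test, exposure 20-40%: 39-44% at 30 v 30 (size 0.022-0.026) and about 30-31% at 15 v 15 (size 0.016-0.017).
- Only the risk-increasing direction counts, 2.5% per test: 1 − 0.975^22 = 43%.

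A fair range is roughly 30-80%. It can be left in both directions. If all 22 markers were binary with 10% exposure and tested exactly at 30 v 30 (size 0.0094), the figure is 1 − 0.9906^22 = 19%. If 64 SNPs were tested singly as independent tests, it is 1 − 0.95^64 = 96%.

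**5. How good a noise score looks.** Each simulated study (4,000 per design) had 20 independent normal markers, none related to DIS. Markers with p < 0.05 by t test were summed with the observed sign, and the AUC was computed in the same data. The true AUC is 0.50. Mean apparent AUC when at least one marker was selected:

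| Cases v controls | Mean apparent AUC |
|---|---|
| 30 v 60 | 0.68 |
| 30 v 30 | 0.70 |
| 15 v 30 | 0.74 |
| 15 v 15 | 0.78 |

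With 22 markers the 30 v 30 and 15 v 15 values are again 0.70 and 0.78.

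**The case against.** The strongest reply is that this is a pilot and says so. Section V.E denies any expectation of settling the question, V.F.a speaks of preliminary data, and V.F.c admits imprecision and points to larger studies. That stands against any claim that the study sets out to confirm an algorithm. It does not supply the missing rule. An exploratory score still needs a stated way of being built and an honest measure of its performance.

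A reader might infer something stronger: that one positive marker is enough to meet the central hypothesis, so that it would be confirmed about two times in three under no effect. The documents do not say this. V.F.c speaks of factors in the plural, and its example combines four. At k = 22, at least two is 30% and at least four is about 2%. A reader might also infer that no result could fail the hypothesis. The same arithmetic refutes that: with 22 null markers, 0.95^22 = 32% of studies would select nothing and yield no score. What is true is that no failure criterion is stated.

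Nor do the documents make an observed odds ratio of 2 a threshold for selection; the two-fold figure in V.F.c is illustrative. They also do not say that a fixed score will be taken unchanged into the multi-centre study: results and stored samples go forward, and the model is to be extended over time.

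Finally, alpha and independence are assumptions, and independence is implausible for the three lipids or for stress, anxiety and depression. That is why a range is given. More-than-even odds of a false selection cannot be claimed as robust.

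**Conclusion.** The point holds in a limited form. The plan selects from about 20 or more markers and builds a score in the same 15-30 cases without defining selection, controlling multiplicity, validating the score or stating what would count against the hypothesis. Under no effect, the chance of at least one false selection is about 64-68% for 20-22 markers, assuming independent two-sided 5% tests. It is roughly 30-80% when correlation, type of test and marker count vary within reason, and 26-30% for at least two markers. The optimism is the more telling figure: a score with true AUC 0.50 would appear at about 0.70 (30 v 30) to 0.78 (15 v 15). This should be put right in the analysis plan. It does not undermine data collection, and it does not show that the study would declare a false confirmation.

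**What to change.** In V.F.c:

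1. List the Aim 2 markers, and fix the selection rule and alpha in advance.
2. Report false-discovery-rate q-values beside the individual marker results.
3. Report the score's performance corrected for selection, by cross-validation or optimism correction, repeating the selection step each time.
4. Compare that performance with a one-sided (upper-tail) permutation distribution. Permute DIS status within the matched DIS-positive/DIS-negative FDR sets and rerun the whole select-and-score procedure each time, counting a run that selects nothing as AUC 0.50. Non-FDR controls stay out of this step because they have no MRI and their DIS status is unknown. Even 15 pairs allow 2^15 = 32,768 arrangements, which is ample.
5. Describe the score as supported only if its performance exceeds the 95th percentile of that distribution. Otherwise report marker estimates with intervals as hypothesis-generating. Put this rule in place of the sentence "we expect that some results will have clinical significance".

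The rule governs how the score is described and does not replace the exploratory estimates. The cost is analysis wording and a short permutation program, with no new data or participants. The drawback is that with 15-30 cases the test may well not reject even if some effects are real, so the claim becomes less favourable.
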